15.1.2 Adverse Events Leading to Discontinuation of Study Treatment

Frequency tables summarizing the following actions taken with study treatment will be presented by PT and primary SOC in alphabetical order:

- TEAEs leading to temporary treatment interruption
- Related TEAEs leading to temporary treatment interruption
- TEAEs leading to permanent treatment discontinuation
- Related TEAEs leading to permanent treatment discontinuation

- TEAEs leading to infusion rate reduction
- Related TEAEs leading to infusion rate reduction

In addition, the incidences for above items will be summarized in an overview table.

The listing of TEAEs leading to permanent treatment discontinuation will also be provided with the relevant information.

15.2 Deaths, Other Serious Adverse Events, and Other Significant Adverse Events

15.2.1 Deaths

All deaths, deaths within 30 days after last dose of study treatment (in case of reinitiated participants, the last dose will be the last dose of the reinitiation phase), death within 60 days after first dose of study treatment (for all participants, the first dose will be the first dose of the first treatment phase) as well as the primary reason for death will be tabulated based on information from the “Death” eCRF pages.

The following summaries will be provided:

- Number of deaths (including deaths during reinitiation phase)
- Number of deaths within 30 days after last dose of study treatment
- Number of deaths within 60 days after first dose of study treatment
- Primary Reason for Death
 - Progressive disease and/or disease related condition
 - Event unrelated to study treatment
 - Event related to study treatment
 - Unknown

In addition, date and cause of death will be provided in an individual participant data listing together with following dosing information: participant identifier, age, sex, race, date of first/last study intervention, number of infusions, day relative to the first and the last infusion, primary reason, autopsy (Y/N/U), AEs with fatal outcome (list PTs of AEs with outcome = Fatal, as well as grade 5 or serious resulting in death), flag for death within 30 days of last dose of study treatment and flag for death within 60 days of first dose of study treatment.

15.2.2 Serious Adverse Events

The following overall frequency tables will be prepared for serious adverse events (SAEs):

- Incidence of serious AEs by SOC and PT
- Incidence of related serious AEs by SOC and PT

The listings of SAEs will also be provided with the relevant information with a flag for TEAEs and AEs occurring during reinitiation phase (see description of listing in section 15.1.1).

15.2.3 Adverse Events of Special Interest

Adverse events of special interest (AESI) are serious or nonserious AEs specific to the known mechanism of action of the study intervention that are of clinical interest. The AESIs considered on this study are: infusion-related reactions including immediate hypersensitivity, immune-related adverse events, skin adverse events, bleeding events and anemia.

15.2.3.1 Infusion-Related Reaction including Immediate Hypersensitivity

Infusion-Related Reactions (IRRs) are defined as adverse events with PTs according to a pre-specified MedDRA search list which will be finalized before database lock, and are divided into two subcategories: “Reactions” and “signs and symptoms” based on criteria on the timely relationship as detailed below:

Reactions of IRR: will be considered when onset is on the day of infusion (during or after the infusion) or the day after the infusion (irrespective of resolution date) for any infusion-related reaction, drug hypersensitivity, anaphylactic reaction, hypersensitivity and/or Type 1 hypersensitivity.

Signs and symptoms of IRRs and hypersensitivity/allergic reactions: will be considered when onset is on the day of infusion (during or after the infusion) and resolved completely with the end date on the same day of the infusion or the day after for any of the following: pyrexia, chills, flushing, hypotension, dyspnea, wheezing, back pain, abdominal pain and urticaria.

IRR, overall and by subcategories, will be summarized by the following variables:

- Number of participants with at least one IRR by the worst NCI-CTCAE toxicity grade (grade 1/ grade 2/ grade 3/ grade 4/ grade 5/ missing grade)
- Number of participants with IRR leading to permanent treatment discontinuation.
- Time related to first onset (infusion 1/ infusion 2/ infusion 3/ infusion 4 or later). The events will be assigned to the actual drug infusions that the participant received, not to the planned dates. An IRR is assigned to a drug infusion if its onset is at the same date and time is missing or same or after dosing (but not before dosing when time is recorded) or the following day of drug infusion.

If at least 10 participants received premedication during the study, IRR will be summarized by premedication (Y/N) subgroups. In this table, the worst grade for each subject will be displayed

for all the IRR started after the use of a premedication and the worst grade for each subject for all the IRR started without the use of a premedication.

The frequency table of IRR and drug related IRR AEs by worst grade, SOC, and PT will also be provided.

The listing of IRRs will be provided with the relevant information (see description of listing in section 15.1.1). One additional listing will display the study drug administration details together with the infusion-related adverse event including administration date (day) /time, reason for modification, type of modification, modification start time, use of pre-medication, IRR AE Preferred Term, IRR AE grade, IRR AE start day /stop day, IRR AE time related to infusion.

15.2.3.2 Immune-Related Adverse Events

Immune-related adverse events (irAEs) will be identified programmatically. AEs which satisfy all of the following criteria will be flagged as immune-related:

- 1) The AE PT matches a PT on the list of pre-selected MedDRA terms.
- 2) The AE onset or worsening occurs after the first study drug administration and no more than 90 days after last dose.
- 3) On the “Adverse Events Details” eCRF page, the question “Were Corticosteroids, Immunosuppressants, or hormonal therapy (e.g. Thyroid) or Insulin applied?” has the answer “Yes” selected.
- 4) On the “imAE Specific Questions” eCRF page, either:
 - a. The question “Does any of the following provide a clear etiology for the event?” has the answer “No” selected, indicating that the AE is not attributable to underlying cancer disease/PD, prior or concomitant medications/procedures, nor another medical condition such as an infection or pre-existing disease.

OR

- b. The “imAE Specific Questions” eCRF page indicates that a biopsy was performed and the question “Is the histopathology/biopsy consistent with an immune-mediated event?” has the answer “Yes” selected.

In the case that criteria (1) through (3) are met, and entries for condition (4) are missing, the following rules will be applied:

- If the answer to “Does any of the following provide a clear etiology for the event?” (4a) is missing, the event will be considered as irAE (irrespective of biopsy results).
- If the answer to “Is the histopathology/biopsy consistent with an immune-mediated event?” (4b) is missing, or if no biopsy was performed, and condition (4a) is not satisfied, i.e. “Yes” is selected (i.e. at least one (clear) etiology of the event is provided) as the answer to the

question “Does any of the following provide a clear etiology for the event?”, the event will be considered as a non-irAE.

PTs will be compiled into categories: Immune-mediated rash, Immune-mediated colitis, Immune-mediated pneumonitis, Immune-mediated hepatitis, Immune-mediated nephritis and renal dysfunction, Immune-mediated endocrinopathies (Adrenal insufficiency, Hypogonadism, Pituitary dysfunction, Type 1 Diabetes Mellitus, Thyroid disorders), Other immune-mediated myositis, Other immune-mediated adverse events. PTs belonging to the category “Immune related endocrinopathies – Thyroid disorders” will also be compiled into sub-subcategories: Hyperthyroidism, Hypothyroidism, Thyroiditis.

Immune-related adverse events (irAEs) will be summarized by the following variables:

- Any irAEs
- irAEs by the worst grade
- irAEs leading to permanent treatment discontinuation
- Serious irAEs

The frequency table of immune-related AEs by worst grade, category, subcategory (for Immune-mediated endocrinopathies), sub-subcategory (for Immune-mediated endocrinopathies – thyroid disorders) and PT will also be provided.

The listing of irAE will also be provided with the relevant information, including additional interventions for irAE (e.g. biopsies, surgical procedures, medical procedures) (see description of listing in section 15.1.1).

15.2.3.3 Potential TGF β Inhibition Mediated Skin Adverse Events

To identify potential skin AEs possibly related to TGF β inhibition, MedDRA PT queries will be used to search for skin AEs of interest in the clinical database. A listing containing these pre-specified PT search terms will be generated. PTs will be compiled into categories: Narrow definition, and Broad definition. Further details (e.g. MedDRA PT queries) are regularly updated based on the current MedDRA version.

Narrow definition:

- Keratoacanthoma
- Squamous cell carcinoma of skin

Broad definition has additional PTs:

- Hyperkerathosis
- Actinic keratosis

- Basal cell carcinoma
- Lip squamous cell carcinoma
- Bowen's disease

The overall summary of potential TGF Beta-mediated skin TEAE will include the following categories for narrow and broad definition:

- All skin TEAE
- All skin TEAE by worst grade
- Skin TEAE leading to permanent treatment discontinuation
- Serious skin TEAEs

Table for skin TEAEs and treatment related skin TEAEs frequency will be provided by MedDRA PTs (including both narrow and broad definition PTs).

A listing of skin AEs will also be provided. This listing will also provide, for the AE identified from the PT list, the number of lesions, if a biopsy or an excision was done and if it confirmed the diagnosis and the lesion location coming from "TGF β Mediated Skin Reaction" eCRF page.

15.2.3.4 Bleeding Events

Bleeding events are those events belonging to the MedDRA SMQ Haemorrhage terms (excluding laboratory terms). Bleeding events and trial drug related bleeding events will be summarized in a frequency table presenting SOC and PT sorted by alphabetical order. The worst grade per participant, per SOC and per PT will be reported: any grade (including missing grade), grade 1, grade 2, grade 3, grade 4 and grade 5. Additionally, a listing of bleeding AEs will be delivered.

15.2.3.5 Anemia

To identify potential anemia AEs MedDRA PT queries will be used to search for these AEs of interest in the clinical database. A listing containing these pre-specified PT search terms provided with the relevant information (see description of listing in section 15.1.1).

The list of PTs includes:

- Anemias NEC (HTL)
- Anemia haemolytic immune (HLT)
- Anemia haemolytic NEC (HLT)
- Haemoglobin decreased (PT)

15.3

Clinical Laboratory Evaluation

Baseline and on-treatment laboratory values (including corresponding normal ranges), converted in standard unit, will be used for boxplots and shift tables.

Laboratory results will be classified according to the NCI-CTCAE criteria version 5.0 and as specified in [Appendix 2 – Definition of NCI-CTCAE grading](#). Additional laboratory results that are not part of NCI-CTCAE will be categorized as follows: below normal limits, within normal limits, and above normal limits (according to the original laboratory normal ranges).

The following figures will be provided for hematology and biochemistry parameters:

- Boxplots of the laboratory values by timepoint
- Boxplots of the change from baseline by timepoint

Boxplots for laboratory parameters where toxicity grades are defined based on the ratio of the parameter values and the upper limit of normal (ULN) will not be displayed using the unit of measurement but instead using the ratio of the measured value over ULN. This comprises alkaline phosphatase (ALP), alanine aminotransferase (ALT), aspartate aminotransferase (AST), activated partial thromboplastin time (aPTT), bilirubin, and creatinine.

Laboratory parameters with NCI-CTC grades available

Laboratory parameters with NCI-CTC grades available will be analyzed with their respective NCI-CTC name and direction of abnormality. For parameters which are graded with both low and high values as potassium (hypokalemia/hyperkalemia), the toxicities will be summarized separately. Low direction toxicity (e.g. hypokalemia) grades at baseline and post-baseline will be set to 0 when the variables are derived for summarizing high direction toxicity (e.g. hyperkalemia), and vice versa.

The following summaries will be displayed:

- Number and percentage of participants by worst on-treatment grade (≥ 1 , ≥ 3 , ≥ 4)
- Shift in toxicity grading from baseline to highest on-treatment toxicity grade

The definitions of the NCI-CTCAE toxicity grading version 5.0 for each parameter are provided in [Appendix 2 – Definition of NCI-CTCAE grading](#) of this IAP.

Table 12 **NCI-CTC Gradable parameters**

Parameter	Parameter code	Name in NCI-CTC	Direction of abnormality
Biochemistry			
Alanine Aminotransferase	ALT	Alanine aminotransferase increased	High
Albumin	ALB	Hypoalbuminemia	Low

Parameter	Parameter code	Name in NCI-CTC	Direction of abnormality
Alkaline Phosphatase	ALP	Alkaline phosphatase increased	High
Amylase	AMYLASE	Serum amylase increased	High
Aspartate Aminotransferase	AST	Aspartate aminotransferase increased	High
Bilirubin total	BILI	Blood bilirubin increased	High
Calcium ^a	CA	Hypercalcemia/Hypocalcemia ^a	High/Low
Creatinine	CREAT	Creatinine increased	High
Glucose	GLUC	Hypoglycemia	Low
Lipase	LIPASET	Lipase increased	High
Potassium	K	Hyperkalemia/Hypokalemia	High/Low
Sodium	SODIUM	Hypernatremia/Hyponatremia	High/Low
Lactate dehydrogenase	LDH	Blood lactate dehydrogenase increased	High
Hematology			
Absolute lymphocyte	LYM	Lymphocyte count decreased/Lymphocyte count increased	High/Low
Absolute eosinophils	EOS	Eosinophilia	High
Absolute neutrophils	NEUT	Neutrophil count decreased	Low
Hemoglobin	HGB	Anemia/Hemoglobin increased	Low/High
Leukocytes (WBC)	WBC	Leukocytosis/White blood cell decreased	High/Low
Platelets count	PLAT	Platelet count decreased	Low
Coagulation			
Activated Partial Thromboplastin Time ^b	APTT	Activated partial thromboplastin time prolonged	High
Prothrombin International Normalized Ratio ^b	INR	INR increased	High
Activated PTT/Standard ^b	APTTSTND	Activated partial thromboplastin time prolonged	High

^a based on corrected calcium (see [Appendix 2 – Definition of NCI-CTCAE grading](#)).

^b reported on the “Coagulation” eCRF page.

For calcium, CTCAE grading is based on corrected calcium. Corrected calcium is calculated from albumin and calcium as follows based on the International System of Units (SI):

Corrected calcium (mmol/L) = measured total calcium (mmol/L) + 0.02 (40 – serum albumin [g/L]).

For **WBC differential counts** (neutrophil, lymphocyte counts), the absolute value will be used when reported. When only percentages are available (this is mainly important for neutrophils and lymphocytes, because the CTCAE grading is based on the absolute counts), the absolute value is derived as follows:

Derived differential absolute count = (WBC count) * (Differential %value / 100)

Laboratory parameters with NCI-CTC grades not available**Table 13 Non-NCI-CTC Gradable Parameters**

Parameter (LBTEST)	Parameter code
Biochemistry	
Bilirubin direct	BILDIR
Bilirubin Indirect	BILIND
Chloride	CL
C-Reactive Protein	CRP
Total Protein	PROT
Urea	UREA
Urea Nitrogen	UREAN
Hematology	
Absolute Basophils	BASO
Absolute Monocytes	MONO
Absolute Reticulocytes	RETI
Basophils/Leukocytes	BASOLE
Eosinophils/Leukocytes	EOSLE
Erythrocytes (RBC)	RBC
Hematocrit	HCT
Lymphocytes/Leukocytes	LYMLE
Mean Corpuscular Hemoglobin	MCH
Mean Corpuscular HGB Concentration	MCHC
Mean Corpuscular Volume	MCV
Monocytes/Leukocytes	MONOLE
Neutrophils/Leukocytes	NEUTLE
Reticulocytes/Erythrocytes	RETIRBC
Coagulation	
Prothrombin Time/Standard Prothrombin Time*	PTS

* reported on the "Coagulation" eCRF page.

For all non-gradable parameters, the following summaries will be displayed:

- Number and percentage of participants by lowest on-treatment value (classified as normal, high, low)
- Number and percentage of participants by highest on-treatment value (classified as normal, high, low)
- Shift from baseline to highest/lowest on-treatment value (classified as normal, high, low)

Separate listings of hematology (including coagulation) and biochemistry will be created. Each listing will include: participant identifier, age, sex, race, first dose date, last dose date, laboratory parameter (units), visit, date, SI value, change from baseline value, lower limit of normal, ULN,

indicator of normal range (low, normal, high), toxicity grade according to NCI-CTCAE (when applicable) and highest/lowest on treatment value flag. Baseline and post-baseline values after the on-treatment period will be flagged. These listings will be sorted by participant identifier, parameter and laboratory measurement date.

Liver function tests

ALT, AST and total bilirubin are used to assess possible drug induced liver toxicity. The ratios of test result over ULN will be calculated and classified for these three parameters during the on-treatment period.

The number and percentage of participants within each of the following liver function categories during on-treatment period will be described:

- ALT < 3×ULN, ALT ≥ 3×ULN, ALT ≥ 5×ULN, ALT ≥ 10×ULN, ALT ≥ 20×ULN
- AST < 3×ULN, AST ≥ 3×ULN, AST ≥ 5×ULN, AST ≥ 10×ULN, AST ≥ 20×ULN
- (ALT and AST) < 3×ULN, (ALT or AST) ≥ 3×ULN, (ALT or AST) ≥ 5×ULN, (ALT or AST) ≥ 10×ULN, (ALT or AST) ≥ 20×ULN
- Total Bilirubin (TBILI) < 2×ULN, TBILI ≥ 2×ULN
- Concurrent ALT ≥ 3×ULN and TBILI ≥ 2×ULN
- Concurrent AST ≥ 3×ULN and TBILI ≥ 2×ULN
- Concurrent (ALT or AST) ≥ 3×ULN and TBILI ≥ 2×ULN
- Concurrent (ALT or AST) ≥ 3×ULN and TBILI ≥ 2×ULN and ALP > 2×ULN
- Concurrent (ALT or AST) ≥ 3×ULN and TBILI ≥ 2×ULN and ALP ≤ 2×ULN or missing

Concurrent measurements are those occurring on the same date.

Categories will be cumulative, i.e., a participant with an elevation of AST ≥ 10×ULN will also appear in the categories ≥ 5×ULN and ≥ 3×ULN.

A plot of peak ALT versus peak total bilirubin, both relative to the ULN will be provided. This eDISH plot (evaluation of drug-induced serious hepatotoxicity) will be divided into 4 quadrants by the lines through ALT ≥ 3×ULN and total bilirubin ≥ 2×ULN. The left lower quadrant is then considered normal or insignificant elevations in liver chemistries, the upper quadrants indicate participants with possible Gilbert's cholestasis; the right upper quadrant are the possible Hy's Law participants; the right lower quadrant is possible Temple's Corollary (participants with ALT ≥ 3×ULN but not satisfying Hy's Law). Same plot will be provided for AST.

In addition, a listing of all total bilirubin, ALT, AST and ALP values for participants with a post-baseline total bilirubin ≥ 2×ULN, ALT ≥ 3×ULN or AST ≥ 3×ULN will be provided.

Urinalysis/urinalysis microscopic evaluation, hormonal tests, tuberculosis test and serology

All test results for urinalysis /urinalysis microscopic evaluation, hormonal tests, serum and serology parameters will also be listed in dedicated listings:

- Urinalysis parameters:
 - Urinalysis full parameters: physical appearance, pH, specific gravity, protein, glucose, ketones, nitrite, leukocyte esterase, blood, urobilinogen, bilirubin, color
 - Urinalysis microscopic parameters: erythrocytes (RBC), leukocytes (WBC), epithelial cells, bacteria, crystals, casts
- Tuberculosis parameters: M. tuberculosis IFN Gamma Response by T-SPOT ELISPOT, Tuberculosis skin test (TST), M. tuberculosis IFN Gamma Response by QuantiFERON TB Gold ELISA
- Hormonal parameters: thyroxine free (Free T4), thyrotropin (Thyroid-Stimulating Hormone; TSH)
- Serology parameters: hepatitis B virus (HBV), hepatitis C virus (HCV), hepatitis B DNA, hepatitis C RNA

Pregnancy test

Results for pregnancy and post-menopausal status as collected on the “Pregnancy Test” eCRF page will also be listed:

- Pregnancy parameters (serum or highly sensitive urine human chorionic gonadotropin [hCG])
- Post-menopausal status: FSH and estradiol parameters

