6.9.2 Immune-related Adverse Events

Immune-related AEs are specific to immunotherapies and vary by organ system. Immune-related AEs are considered AESIs.

In general, the spectrum of irAEs is similar for bintrafusp alfa compared with other checkpoint inhibitors. Effective risk management of these toxicities (irAEs) primarily caused due to inhibition of PD-L1 and PD-1 pathways is based on key recommendations (Champiat 2016). Participant education for on-time reporting of symptoms of potential irAEs and prompt clinical assessment is critical for effective management and quicker resolution of immune-mediated toxicities, thus preventing progression into severe forms of toxicity that otherwise may become life-threatening and difficult to manage or warrant permanent discontinuation from the study.

The following irAEs are important identified risks for bintrafusp alfa

- Immune-related hepatitis
- Immune-related pneumonitis
- Immune-related colitis
- Immune-related nephritis and renal dysfunction
- Immune-related endocrinopathies (thyroid disorders, adrenal insufficiency, Type 1 diabetes mellitus, pituitary disorders)
- Immune-related rash
- Other immune-related events (myositis, myocarditis, encephalitis).

The following irAEs are important potential risks for bintrafusp alfa:

- Guillain-Barré syndrome
- Uveitis
- Pancreatitis
- Myasthenia gravis/myasthenic syndrome.

The Medical Monitor may be involved as needed for follow-up. Details of the diagnostic work-up will be requested by the study team.

Recommended guidance and management for specific irAEs as per published guidelines are provided in [Appendix 5](#). These recommendations are in accordance with the joint ASCO Clinical Practice Guidelines ([Brahmer 2018](#)) and National Comprehensive Cancer Network ([NCCN 2018](#)) guidelines.

Treatment of irAEs is mainly dependent upon severity as defined by NCI-CTCAE v5.0. In general, management by NCI-CTCAE v5.0 grading is listed below:

- Grade 1: study intervention should be continued with close monitoring, with the exception of some neurologic, hematologic, and cardiac toxicities.
- Grade 2: study intervention may be suspended for most Grade 2 toxicities, with consideration of resuming when symptoms revert to Grade 1 or less. Corticosteroids may be administered (initial dose of 0.5 to 1 mg/kg/day of prednisone or equivalent).

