Secondary Occurrence of TEAEs and treatment-related AEs	
The safety endpoints will be tabulated using descriptive statistics.
 
Participants will be analyzed according to the actual treatment they receive.The safety endpoints will be analyzed using descriptive statistics.The incidence of TEAEs, SAEs, treatment-related AEs, AESIs, and irAEs will be summarized by preferred term and system organ class for each treatment arm, and described in terms of severity and relationship to treatment.The worst on-treatment grades for chemistry and hematology laboratory results will be summarized.Shifts in toxicity grading from Baseline to highest grade during the on-treatment period will be displayed.For laboratory tests without an NCI-CTCAE grade definition results will be presented categorically (e.g., below, within, or above normal limits). 
Further details of safety analyses (including AEs, clinical laboratory assessments, vital signs, physical examination, ECG parameters, and ECOG PS) will be provided in the IAP.

AE=adverse event, AESI=adverse event of special interest, ECG=electrocardiogram, ECOG PS=Eastern Cooperative Oncology Group performance status, IAP=Integrated Analysis Plan, irAE=immune-related adverse event, NCI-CTCAE=National Cancer Institute Common Terminology Criteria for Adverse Events, SAE=serious adverse event, TEAE=treatment-emergent adverse event.

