4.4 Diabetes

Definition: T2DM is a combination of insulin resistance and insufficiency that may require oral or insulin therapy. It may be new onset or exacerbated during therapy for nonimmunologic reasons, such as corticosteroid exposure.

Autoimmune T1DM results from islet cell destruction and is often acute onset, with ketosis and an insulin requirement

Diagnostic work-up

Monitor patients for hyperglycemia or other signs and symptoms of new or worsening DM, including measuring glucose at baseline and with each treatment cycle during induction for 12 weeks, then every 3-6 weeks thereafter. To guide the work-up in new-onset hyperglycemia, clinicians should consider a patient's medical background, exposure history, and risk factors for each subtype of DM.

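### No planned laboratory grade, worst-value or shift table covers high glucose (SAP Table 12 grades it low only, Table 13 omits it), and TSH and free T4 are only listed

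*SAP*

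**What the plan says.** SAP 15.3 divides laboratory tests into two groups. Table 12 holds the CTCAE-gradable parameters, and the rule for them is: "Laboratory parameters with NCI-CTC grades available will be analyzed with their respective NCI-CTC name and direction of abnormality". Their outputs are "Number and percentage of participants by worst on-treatment grade" and a shift from baseline grade to highest on-treatment grade. The glucose row reads "Glucose GLUC Hypoglycemia Low". Parameters meant to be graded both ways are marked so; potassium, for example, reads "Hyperkalemia/Hypokalemia High/Low".

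Table 13 holds the non-gradable parameters. They are summarised by lowest and highest on-treatment value (low, normal, high) and by shift from baseline. Glucose, TSH and free T4 are not in it. The two thyroid tests appear only under the dedicated listings: "Hormonal parameters: thyroxine free (Free T4), thyrotropin (Thyroid-Stimulating Hormone; TSH".

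Protocol 9.4.2, Table 12, says: "For laboratory tests without an NCI-CTCAE grade definition results will be presented categorically (e.g., below, within, or above normal limits". Protocol 6.9.2 includes among the important identified risks "Immune-related endocrinopathies (thyroid disorders, adrenal insufficiency, Type 1 diabetes mellitus, pituitary disorders". Protocol Appendix 5, section 4.4, tells sites: "Monitor patients for hyperglycemia or other signs and symptoms of new or worsening DM". Glucose is in the biochemistry panel of Protocol Appendix 6.

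**The concern.** For glucose, the direction tied to a named drug risk is the one with no laboratory summary. A reader of the planned tables would see a hypoglycemia grade and a hypoglycemia shift and nothing about rising glucose. TSH and free T4, which bear on the thyroid part of the same risk, have no laboratory summary in either direction.

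Adverse event tables do not fully stand in for this. Protocol Appendix 4 keeps abnormal laboratory findings out of adverse event reporting unless they come with clinical signs or symptoms, lead to discontinuation of study intervention, or are judged medically important. Laboratory summaries pick up what that filter leaves out. At stake is the completeness of the laboratory safety tables for an important identified risk. No efficacy result is touched.

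**Working it through.** No sample size, power or error rate bears on this, and the plan states no figure to reproduce. The check is a row count and a trace of each planned output.

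**Rows in SAP Table 12 (gradable).** 13 biochemistry + 6 hematology + 3 coagulation = 22. Six are two-directional: calcium, potassium, sodium, lymphocytes, hemoglobin and leukocytes. Glucose has one row, low only. The table thus has a notation for two-way grading and does not use it for glucose.

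**Rows in SAP Table 13 (non-gradable).** 7 biochemistry + 14 hematology + 1 coagulation = 22. There is no glucose, TSH or free T4 row.

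**Where a high serum glucose goes:**

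- Worst on-treatment grade: follows the listed direction, so low values only. Not covered.
- Grade shift: same rule. Not covered.
- Highest or lowest on-treatment value: Table 13 parameters only. Not covered.
- Normal-range shift: Table 13 parameters only. Not covered.
- Boxplots of values and of change from baseline: all biochemistry. Covered.
- Biochemistry listing: carries the upper limit of normal, change from baseline, a low/normal/high indicator and a highest/lowest flag. Covered.

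The number of laboratory grade, worst-value or shift tables that cover high glucose is 0.

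**Illustration (assumed values).** Suppose baseline is 90 mg/dL and the worst value is 510 mg/dL, which is above the 500 mg/dL bound of the highest band in Appendix 5, section 4.4. Neither value is low, so the hypoglycemia tables correctly show no abnormality at either point. The listing marks the second value as high.

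**Adverse event route.** SAP 15.2.3.2 flags an immune-related event only if four things hold:

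1. The preferred term is on the search list.
2. Onset or worsening falls after first dose and within 90 days of last dose.
3. The question on corticosteroids, immunosuppressants, hormonal therapy or insulin is answered yes.
4. No clear other etiology is recorded, or a biopsy supports an immune cause (a missing etiology answer counts as immune-related).

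Type 1 diabetes is a named subcategory, so a diagnosed case given insulin would normally be tabulated. Two kinds of case can miss this route: high glucose without symptoms, which may never be reported as an adverse event, and a case managed with oral therapy alone, an option Appendix 5 mentions for Type 2 disease, which fails the third condition.

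**TSH and free T4.** Protocol Table 1 schedules them at screening and repeatedly on treatment. The SAP gives them no grade in Table 12, so on its own classification they fall under the protocol's rule for ungraded tests. They are not in Table 13 either, and the hormone listing names no range indicator, unlike the biochemistry listing.

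**The case against.** Five arguments weigh on the other side.

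- **The tables are largely superseded.** SAP 4.1 records early discontinuation and allows listings in place of summary tables, as deemed appropriate, in an abbreviated report. This stands and is the main reason the point is minor.
- **The risk is tabulated elsewhere.** Type 1 diabetes and thyroid disorders have their own immune-related categories, all treatment-emergent events are tabulated by preferred term, and Protocol 8.2.4 has investigators record clinically relevant laboratory changes as adverse events. This stands for diagnosed or reported cases. A reader might infer from Tables 12 and 13 that every case of hyperglycemia disappears from the tables. The documents do not support that: the gap is confined to the laboratory tables, and the listing and boxplots still show the values.
- **There is no protocol breach for glucose.** A reader might infer that the SAP violates Protocol Table 12 here. That sentence concerns tests with no CTCAE grade definition, and glucose has one in the low direction, so it does not literally reach glucose. SAP 15.3 also has a general sentence that categorises results outside CTCAE by normal limits. It could be read to include high glucose, but the outputs that would carry it out are tied to Table 13. For TSH and free T4 the protocol sentence does apply.
- **The entry may be deliberate.** The SAP's modification history for version 2.0 says the glucose direction was updated, so calling it an oversight would go too far. A deliberate choice still leaves high values without a companion row.
- **The grading definitions are not visible.** SAP Appendix 2 is not reproduced in the text available. This limits what can be said about its content, but 15.3 ties the analysis to the direction shown in Table 12.

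**Conclusion.** The point holds in a limited form and is minor. As written, high glucose enters no planned laboratory worst-grade, worst-value or shift table. TSH and free T4 have no laboratory summary table at all, which for them departs from Protocol Table 12. High glucose stays visible in boxplots and the biochemistry listing, and diabetes meeting the immune-related criteria is tabulated. The residual gap is asymptomatic high glucose, or cases not treated with any of the qualifying therapies.

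No percentage of participants can usefully be attached: SAP 4.1 says only that the number of participants is low, and the planned 29 is not the right denominator after early discontinuation. The conclusion assumes that SAP 15.3 is implemented as its tables read and that Appendix 2 does not add a high direction for glucose.

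**What to change.** - Add glucose to SAP Table 13 for the high direction (highest on-treatment value and shift by normal range), and keep the Hypoglycemia row in Table 12. A footnote should explain why glucose appears in both tables.
- Add TSH and free T4 to Table 13.
- For the abbreviated report, add a low/normal/high indicator to the hormone listing. The biochemistry listing already has one, so it needs no change for glucose.

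Do not build a high-glucose scale from the bands in Protocol Appendix 5, section 4.4. They are management criteria that mix fasting glucose with symptoms, daily function and ketosis. The Appendix 6 panel lists glucose with no fasting requirement, and Protocol 5.3 sets no dietary restriction. They would also put a second scale inside a table defined by CTCAE.

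The cost is three table rows, one footnote and one listing column. The tests are already collected, and Protocol 8.2.4 already requires local normal ranges to be sent to the sponsor.
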